Mode of administration	
All modes of administration during the Humira treatment period should be summarized, and indicated by five levels of category:
 
administration by a physician only, administration by a physician to self-administration, self-administration only, self-administration to administration by a physician, and administration by a physician and self-administration alternatively.
 
When tabulating, the patients should be categorized by “administration by a physician only” for patients who received Humira by administration by a physician only, “self-administration only” for patients with self-administration only, and “administration by a physician and self-administration” for patients received in both modes of administration and should be tabulated by group.

Dosage and administration	
Dosage and administration should be indicated by the following four levels of categories:
 
40 mg/biweekly, 80 mg/biweekly, 40 mg/biweekly or 80 mg/biweekly, other
 
.

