Reason for discontinuation (third CRF)	Occurrence of AEs, symptom improved, inadequate response, patient refused treatment with Humira, others (pregnancy/desire for pregnancy, others), undescribed
Reason for survey discontinuation	Administration of biological products other than Humira, failed to visit hospital, others, undescribed

<Efficacy endpoints>

Data	Layer separation	
DAS28-4ESR	High Moderate Low Remission	> 5.1 > 3.2 and ≤ 5.1 ≥ 2.6 and ≤ 3.2 < 2.6
DAS28-4CRP	High Moderate Low Remission	> 5.1 > 3.2 and ≤ 5.1 ≥ 2.6 and ≤ 3.2 < 2.6
CDAI	High Moderate Low Remission	> 22.0 > 10.0 and ≤ 22.0 > 2.8 and ≤ 10.0 ≤ 2.8
SDAI	High Moderate Low Remission	> 26.0 > 11.0 and ≤ 26.0 > 3.3 and ≤ 11.0 ≤ 3.3
HAQ-DI	High Moderate Low Remission	> 1.5 > 1.0 and ≤ 1.5 > 0.5 and ≤ 1.0 ≥ 0 and ≤ 0.5
mTSS	Change (≤ 0) Change (≤ 0.5) Change (≤ 1.0)	Change ≤ 0 Change ≤ 0.5 Change ≤ 1.0
Bone erosion score	Change (≤ 0) Change (≤ 0.5) Change (≤ 1.0)	Change ≤ 0 Change ≤ 0.5 Change ≤ 1.0
Joint space narrowing score	Change (≤ 0) Change (≤ 0.5) Change (≤ 1.0)	Change ≤ 0 Change ≤ 0.5 Change ≤ 1.0

*Hereafter, “complete remission” refers to “Remission” in the above table.

12. Handling of data on test/evaluation time

For data entered at each timing of efficacy evaluation excluding mTSS, bone erosion score and joint space narrowing score, the acceptability of data by timing should be judged based on the acceptable range of the timing. The acceptable range of the timing is shown in the table below.

If there is more than one data within the acceptable range of the timing, the data on the closest date to the reference date should be adopted. If there is more than one data within the acceptable range of the timing with the equal number of days from the reference before and after the reference date respectively, the data before the reference date should be adopted.

When evaluating efficacy regarding administration of Humira, it should follow the following provision for the data included in the following acceptable range.

- The data up to the date of final Humira treatment + 28 days should be tabulated.

However, the date of final Humira treatment +28 days is later than the date of survey discontinuation, the data up to the date of survey discontinuation should be tabulated.

This date is called [final evaluation date] in the following.

Timing and period category	Handling of data

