Prior to treatment start	Data included in the period between the date of initial Humira treatment -28 days and the date of initial Humira treatment and the closest data to the date of initial Humira treatment should be adopted.
At week 12	Data included in the period between the date of initial Humira treatment +56 days and the date of initial Humira treatment +112 days and the closest data to the date of initial Humira treatment +84 days should be adopted.
At week 24	Data included in the period between the date of initial Humira treatment +140 days and the date of initial Humira treatment +196 days and the closest data to the date of initial Humira treatment +168 days should be adopted.
At week 52	Data included in the period between the date of initial Humira treatment +336 days and the date of initial Humira treatment +392 days and the closest data to the date of initial Humira treatment +364 days should be adopted.
At week 76	Data included in the period between the date of initial Humira treatment +504 days and the date of initial Humira treatment +560 days and the closest data to the date of initial Humira treatment +532 days should be adopted.
At week 104	Data included in the period between the date of initial Humira treatment +700 days and the date of initial Humira treatment +756 days and the closest data to the date of initial Humira treatment +728 days should be adopted.
At final evaluation	The final data of the patient among the data included in the period between the date of initial Humira treatment +1 day and the final evaluation date should be adopted.

For data entered at each evaluation timing of mTSS, bone erosion score and joint space narrowing score when evaluating efficacy regarding administration of Humira, the acceptability of data by timing should be judged based on the acceptable range of the timing. The acceptable range of the timing is shown in the table below.

If there is more than one data within the acceptable range of the timing, the data on the closest date to the reference date should be adopted. If there is more than one data within the acceptable range of the timing with the equal number of days from the reference before and after the reference date respectively, the data before the reference date should be adopted.

Additionally, it should follow the following provision for the data included in the following acceptable range.

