Purpose of analysis: To indicate the number of overall patients with fixed CRFs and by CRF for the patients included in the safety analysis set and efficacy analysis set.

Note: None in particular.

“Table 1.3.2 List of patients”

Analysis object: Patients with fixed CRFs

Purpose of analysis: To confirm the details of the overall patients.

Note: To indicate the details in a list.

“Table 1.3.3 Lists of patients excluded from safety analysis set and patients excluded from efficacy analysis set (including reasons for exclusion)”

Analysis object: Patients excluded from the safety analysis set, patients excluded from the efficacy analysis set

Purpose of analysis: To confirm the reasons for excluding from the safety analysis set and efficacy analysis set.

Note: To indicate the case numbers and reasons for exclusion in a list.

<Detailed note>

*Where one patient has more than one reason for exclusion, they should be linked with “commas” for output.

“Table 1.4 Disposition by Hospital of the University of Occupational and Environmental Health, Japan”

Analysis object: Patients included in the safety analysis set, patients included in the efficacy analysis set (DAS28-4CRP)

Purpose of analysis: To indicate the incidence of ADRs and the results of χ^2 tests in the patients included in the safety analysis set and the response rate in EULAR DAS28-4CRP and the results of χ^2 tests in EULAR DAS28-4CRP at the final evaluation in patients included in the efficacy analysis set (DAS28-4CRP) per institution analyzed (other than Hospital of the University of Occupational and Environmental Health, Japan and University of

Occupational and Environmental Health, Japan).

Note: Good Response and Moderate Response should be judged as “effective” for the EULAR DAS28-4CRP response at the final evaluation.

“Table 1.5 Disposition by mode of Humira administration”

Analysis object: Patients included in the safety analysis set, patients included in the efficacy analysis set (DAS28-4CRP)

Purpose of analysis: To indicate the incidence of ADRs and the results of χ^2 tests in the patients included in the safety analysis set and the response rate in EULAR DAS28-4CRP and the results of χ^2 tests at the final evaluation in patients included in the efficacy analysis set (DAS28-4CRP).

The category for mode of administration should follow “11. Data-layer separation.”

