Note: The information on novelty should not be granted. This should be prepared only when there are more than ten patients or 3% of the patients are applicable to the category of interest.

The next forms should be prepared in the same manner.

“Table 5.5.1.2 Frequency of ADRs by seriousness with or without renal disorder”

Note: The categories of the tabulation should be with or without renal disorder.

“Table 5.5.1.3 Frequency of ADRs by seriousness in elderly or non-elderly”

Note: The categories of the tabulation should be by elderly or non-elderly.

“Table 5.5.1.4 Frequency of ADRs by seriousness by mode of Humira administration”

Note: The categories of the tabulation should follow the mode of Humira administration in Table 3.1.

“Table 5.5.2.1 Frequency of ADRs by outcome with or without liver disorder”

Analysis object: Patients included in the safety analysis set

Purpose of analysis: to indicate the number of patients analyzed, number of patients who developed all ADRs, number and percentage of ADRs, number and percentage of SOC and PT with or without liver disorder by outcome regarding ADRs.

Note: The information on novelty should not be granted.

This should be prepared only when there are more than ten patients or 3% of the patients are applicable to the category of interest.

The next forms should be prepared in the same manner.

“Table 5.5.2.2 Frequency of ADRs by outcome with or without renal disorder”

Note: The categories of the tabulation should be with or without renal disorder.

“Table 5.5.2.3 Frequency of ADRs by outcome by elderly or non-elderly”

Note: The categories of the tabulation should be by elderly or non-elderly.

“Table 5.5.2.4 Frequency of ADRs by outcome by mode of Humira administration”

Note: The categories of the tabulation should follow the mode of Humira administration in Table 3.1.

“Table 5.6 Appended Form 2”

Analysis object: Patients included in the safety analysis set

Purpose of analysis: To prepare for reexamination.

Note: None in particular.

“Table 5.7 Appended Form 3”

Analysis object: Patients with fixed CRFs

Purpose of analysis: To indicate a list of summaries of the patients surveyed.

Note: A specification should be prepared separately for the details of analysis specification.

“Table 5.8.1 The Number of Weeks to Discontinuation”

Analysis object: Patients included in the safety analysis set

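### Table 1.5 tests a mode-of-administration class that depends on time on drug, so its chi-square tests can exceed 5% when mode has no effect

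*SAP*

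**What the plan says.** SAP 10.1 (Mode of administration) builds the class from everything that happened on treatment: "All modes of administration during the Humira treatment period should be summarized, and indicated by five levels of category". For tabulation the five levels become three: physician only, self only, and a mixed group "for patients received in both modes of administration and should be tabulated by group".

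The SAP uses this class in four places.

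- **Table 3.1** describes use.
- **"Table 1.5 Disposition by mode of Humira administration"** (SAP 13.1) gives ADR incidence and EULAR DAS28-4CRP response at the final evaluation, each with a chi-square test.
- **Tables 5.5.1.4 and 5.5.2.4** (SAP 13.2) give ADR frequencies by seriousness and by outcome. For these, "The categories of the tabulation should follow the mode of Humira administration in Table 3.1". No test is named.

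Final evaluation is not a fixed visit. SAP section 12 takes "The final data of the patient among the data included in the period" from the day after first dose to the final evaluation date, and cuts the data off as follows: "The data up to the date of final Humira treatment + 28 days should be tabulated" (or at survey discontinuation, if earlier).

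SAP 9.6 calls p < 0.05, two-sided, significant.

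**The concern.** The grouping variable is settled by the future. At first dose nobody is in the both-modes group. A patient enters it by remaining on Humira until the mode changes, and anyone who stops before then stays in a single-mode group. This is the usual structure of immortal-time bias.

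The documents link time on drug to both tested outcomes:

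- SAP section 11 lists adverse events and inadequate response among the reasons for stopping.
- Under protocol 7.5, stopping adalimumab in the first 52 weeks ends the patient's participation. Protocol 12.0 documents adverse events only to week 104 or discontinuation of the study. Early stoppers therefore have less time in which an ADR can be recorded.
- Attrition is expected to be heavy: about 32% at week 24 in the earlier all-case survey, and 50% assumed at week 52 (protocol 13.1, SAP 4.3).

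No class fixed at the start of treatment and no exposure-adjusted rate is planned by mode. The only rate per patient-years is by baseline MTX dose (Table 5.2.4).

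SAP 3.1 says the results serve reports to authorities and the reexamination application. A small p-value in Table 1.5 could be read there as a property of the injection route when time on drug alone can produce it.

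**Working it through.** **Plan's own figure.** The documents give none for the mode tests. From the plan come N = 350 (171/(1 − 0.50) = 342, rounded up), alpha 0.05 two-sided, and the expected attrition. Everything else below is an assumption.

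**Base assumptions, no effect of mode.** All patients start with physician injection; 60% would switch, with a median of 8 weeks if still treated; 75% are responders; 62% of responders and 20% of non-responders are retained at week 52 before ADR stops; ADR hazard 0.4/year; 30% of ADRs stop treatment; follow-up is 104 weeks. Retention at week 52 is (0.75 × 0.62 + 0.25 × 0.20) × exp(−0.12) = 0.515 × 0.887 = 46%, near the plan's 50%.

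**Response, by hand (ignoring ADR stops).**

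1. Weekly hazards: responders stop at −ln(0.62)/52 = 0.00919; non-responders stop at −ln(0.20)/52 = 0.03095; switching is ln(2)/8 = 0.08664.
2. Chance that a would-be switcher switches before stopping: 0.08664/(0.08664 + 0.00919) = 0.904 for responders and 0.08664/(0.08664 + 0.03095) = 0.737 for non-responders.
3. Both-modes group: responders 0.75 × 0.60 × 0.904 = 0.407; non-responders 0.25 × 0.60 × 0.737 = 0.111. Response is 0.407/0.517 = 78.6%.
4. Physician only: responders 0.343 of 0.483 in all, or 71.1%.
5. With 181 and 169 patients, the standard error is √[0.75 × 0.25 × (1/181 + 1/169)] = 0.0463. The spurious difference of 0.075 is 1.63 standard errors, and a 5% test rejects with probability about 37%.

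**Simulation.** With ADR stops included, the base case gives, for both modes v physician only: response 79% v 71%, ADR 36% v 30%, time on drug 62 v 45 weeks. The table shows the share of 2,000 simulated studies with p < 0.05 (simulation error about ±2 points), each row changing only what is named.

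| Assumption | ADR test | Response test |
|---|---|---|
| Base | 22% | 35% |
| No ADR stops treatment | 40% | 37% |
| Half of ADRs stop treatment | 11% | 33% |
| All ADRs stop treatment | 5% | 30% |
| 30% would switch | 10% | 13% |
| Retention 55% v 35% (weaker link) | 19% | 10% |
| Equal retention, 50% v 50% (no link) | 18% | 5% |
| 40% start on self-injection, 60% would switch, three groups | 15% | 28% |
| 40% start on self-injection, 30% would switch, three groups | 9% | 11% |
| 40% start on self-injection, classed by first-injection mode | 5% | 5% |

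Repeat runs differ by a point or so. If all ADRs stop treatment, the ADR difference reverses slightly (33% in both modes v 34% in physician only).

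**Outside this range.** The range is not a ceiling. Later switching (median 26 weeks) gives about 41% for ADR and about 70% for response. A separate set of runs used 32% attrition by week 24 and 50% by week 52. It assumed a strong link: 90% response if treated for at least 52 weeks, 50% if not. The response test then rejected in 22-97% of studies. With almost no switching (2% by week 24) the same set gave 6% for ADR and 8% for response.

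**Limit.** The simulations count on-treatment ADRs only. The SAP keeps ADRs to day 755, including some after stopping, which would weaken the exposure link somewhat.

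**The case against.** The strongest reply is that nothing in the documents fixes the size. They give no switching rate, starting-mode split or ADR rate. Even in the base case the tests do not reject in 78% (ADR) and 65% (response) of studies. For ADRs two forces oppose each other: longer exposure adds ADRs to the both-modes group, while ADR-driven stopping removes patients before they can switch. All of this stands. A reader might infer that Table 1.5 will report false differences, or that one of the simulated figures is its false-positive rate. The documents support neither.

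A second reply concerns what is distorted. When patients switch at similar rates from either starting mode, physician-only and self-only have the same expected results (ADR 32% in each and response 74% in each, with 40% starting on self-injection and 30% switching). So it does not follow that Table 1.5 must make self-injection look better or worse than physician injection; the distortion falls mainly on the both-modes group. The single-mode groups can also part if switching runs mainly one way, but the documents do not say that it does.

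A third reply concerns scope. Table 1.5 is a disposition table on which no decision rule rests. It would be wrong to read Tables 5.5.1.4 and 5.5.2.4 as tested comparisons, or the week-52 remission result as affected. That also stands.

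None of this removes the defect: a class that depends on treatment duration is tested against outcomes that depend on it too, and no section corrects for that.

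**Conclusion.** The concern holds for the two chi-square tests in Table 1.5. With no effect of mode, the response test rejects in about 10-37% of studies and falls to about 5% if response is unrelated to retention. The ADR test rejects in about 5-41%, with a direction that can reverse. These figures rest on assumed inputs: 30-60% would switch, with a median of 8 weeks; 0-40% start on self-injection; 0-100% of ADRs stop treatment; and a weaker or stronger link between response and retention. Later switching or a stronger link raises them, and rare switching lowers them. The response half is the firmer one, because inadequate response is a listed reason for stopping and the endpoint is the last value on treatment. In Tables 5.5.1.4 and 5.5.2.4 the same classes affect how frequencies read, not a test.

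**What to change.** 1. **Table 1.5:** test by mode at first injection, if both starting modes occur in useful numbers. Otherwise report the whole-period classes without p-values. The five-level coding in SAP 10.1 already separates physician-to-self from self-to-physician, so first mode should be derivable from data already collected.
2. **Tables 3.1, 5.5.1.4 and 5.5.2.4:** keep the whole-period classes as description, with a note that membership of the both-modes group implies longer treatment.
3. **ADR rates:** add rates per 100 patient-years by mode, as Table 5.2.4 does for serious ADRs by MTX dose. If record dates allow, count time and ADRs to the mode in use, since rates by whole-period class correct for unequal exposure but not for who stays long enough to switch.
4. **No week-12 landmark in the safety tables:** it would drop early ADRs from the description.

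The cost is a few lines of SAP text and one derivation. The changed-mode group is no longer tested, and if nearly all patients start in one mode there is no tested comparison.

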10.2. Safety analysis

Name of data	Derivation and calculation methods
Adverse event	For adverse event-related data, “an AE matching list”, the data set through the matching activities (matching of CRF data and safety information data), should be used. AEs with the same patient number should be aggravated and counted as one event when the PT is the same. However, when the novelty (known/unknown) is different within the same PT, such as in Appended Form 2, they should be tabulated separately.
Seriousness of AE	For seriousness of an AE aggravated from a single patient as the same PT, seriousness set through AE matching activities should be set in the following order of priority. Serious Non-serious
Causal relationship of AE	Where the causal relationship set through AE matching is other than “not related”, the causal relationship is defined as related. For causal relationship of an AE aggravated from a single patient as the same PT, causal relationship set through AE matching activities should be set in the following order of priority. Related Not related
Outcome of AE	Outcomes of AEs aggravated from a single patient as the same PT should be set in the following order of priority. Fatal Unknown Not recovered/Not resolved Recovered/Resolved with sequelae Recovering/Resolving Recovered/Resolved
Adverse reaction	AEs of which causal relationship is other than “not related” set through the AE matching activities are defined as ADRs.
Serious AEs	AEs of which seriousness set through the AE matching activities is “serious” are defined as serious AEs.
AEs outside the follow-up period	These should be handled as outside the safety analysis. AEs are defined that occurred prior to the start date of Humira treatment or at week 108 (treatment start date + 755).

10.3. Efficacy analysis

Name of data	Derivation and calculation methods
HAQ disability index	It should be calculated by the following formula. $HAQ = ((A)+(B)+(C)+(D)+(E)+(F)+(G)+(H))/\text{responded number of categories}$ 
 (A) Dressing and grooming (2 items in total) (B) Arising (2 items in total) (C) Eating (3 items in total) (D) Walking (2 items in total)

Name of data	Derivation and calculation methods
	(E) Hygiene (3 items in total) (F) Reach (2 items in total) (G) Grip (3 items in total) (H) Activity (3 items in total) At least 6 categories are required for calculation of HAQ. The highest score among the questions within the category should be adopted for the value of the categories from (A) through (H).
EQ-5D	The score should be calculated by means of “Japanese EQ-5D utility conversion table” <Reference 1> for the following items. (A) Mobility (B) Self-care (C) Usual activities (D) Pain/Discomfort (E) Anxiety/Depression <Reference 1> The Development Committee of the Japanese EuroQol Instrument (1998). 8.109-123. Journal of Health Care and Society
DAS28-4ESR	It should be calculated by the following formula. $\text{DAS28-4ESR} = 0.56 \times \sqrt{(A)} + 0.28 \times \sqrt{(B)} + 0.70 \times \ln(C) + 0.014 \times (D)$ (A) Number of joints with tenderness (a total of 28 joints from left and right shoulders, elbows, hands and knees) (B) Number of swollen joints (a total of 28 joints from left and right shoulders, elbows, hands and knees) (C) Erythrocyte sedimentation rate (ESR) at 1 hour (mm) (D) Global assessments of disease activity by the patient (VAS) (mm)
DAS28-4CRP	It should be calculated by the following formula. $\text{DAS28-4CRP} = 0.56 \times \sqrt{(A)} + 0.28 \times \sqrt{(B)} + 0.36 \times \ln(((E) \times 10) + 1) + 0.014 \times (D) + 0.96$ Refer to (A), (B) and (D) DAS28-4ESR (E) C-reactive protein (CRP) (mg/dL)

Name of data	Derivation and calculation methods																					
EULAR judgement criteria for response	
Both DAS28-4ESR and DAS28-4CRP should be evaluated in accordance with the following table.
 
  
 	EULAR DAS28 response	
 
 >1.2	0.6< ≤1.2	≤0.6	
   
 DAS28 at the evaluation time	≤3.2	Good response	Moderate response	No response	
 
 3.2< ≤5.1	Moderate response	Moderate response	No response	
 
 >5.1	Moderate response	No response	No response	
  
 
DAS28 response should be calculated from the EULAR DAS28 response (DAS28 of the origin) - (DAS28 at evaluation point). Good Response, Moderate Response, or No Response should be judged based on the DAS28 and the response at the evaluation time. Good Response and Moderate Response should be considered effective, and No Response as ineffective.
			EULAR DAS28 response			>1.2	0.6< ≤1.2	≤0.6	DAS28 at the evaluation time	≤3.2	Good response	Moderate response	No response	3.2< ≤5.1	Moderate response	Moderate response	No response	>5.1	Moderate response	No response	No response
				EULAR DAS28 response																		
		>1.2	0.6< ≤1.2	≤0.6																		
DAS28 at the evaluation time	≤3.2	Good response	Moderate response	No response																		
	3.2< ≤5.1	Moderate response	Moderate response	No response																		
	>5.1	Moderate response	No response	No response																		
SDAI	
It should be calculated by the following formula. $SDAI=(A)+(B)+(D)/10+(F)/10+(E)$ Refer to (A), (B) and (D) DAS28-4ESR (E) C-reactive protein (CRP) (mg/dL) (F) Global assessments of disease activity by the physician (VAS) (mm)
																					
CDAI	
It should be calculated by the following formula. $CDAI=(A)+(B)+(D)/10+(F)/10$ Refer to (A), (B) and (D) DAS28-4ESR (F) Global assessments of disease activity by the physician (VAS) (mm)
																					
Bone erosion score	
Based on the reading session score table received from the sponsor, it should be calculated from the scores from two persons (or including the score by the third person) entered in the column of bone erosion.
 
Bone erosion score = the mean of the scores from two persons (when the score from the third person is obtained, two selected persons including the third person)
																					
Joint space narrowing score	
Based on the reading session score table received from the sponsor, it should be calculated from the scores from two persons (or including the score by the third person) entered in the column of JSN.
 
Joint space narrowing score = the mean of the scores from two persons (when the score from the third person is obtained, two selected persons including the third person)
																					
mTSS	
Based on the reading session score table received from the sponsor, it should be calculated from the scores from two persons (or including the score by the
																					

Name of data	Derivation and calculation methods
	third person) entered in the column of total. mTSS = the mean of the scores from two persons (when the score from the third person is obtained, two selected persons including the third person)

11. Data-layer separation

<Patient background characteristics>

Data	Layer separation
Consultation category	Inpatient, outpatient, undescribed
Gender	Male, female, undescribed
Pregnancy/lactation (female)	Other than pregnant or lactating, pregnant, lactating, unknown, undescribed
Age (years)	Children (aged < 15 years), adults (aged ≥ 15 years and < 65 years), elderly (aged ≥ 65 years), undescribed (less than 15, 15 – 30, 30 – 50, 50 – 65, 65 – 75, 75 – 85, equal or more than 85, Unknown/Missing)*3
Weight (kg)	< 30, ≥ 30 and < 40, ≥ 40 and < 50, ≥ 50 and < 60, ≥ 60, unknown, undescribed
Duration of illness (month)	< 3, ≥ 3 and < 6, ≥ 6, unknown, undescribed
Complication	Present, absent, undescribed
Complication (liver disorder)	Hepatitis, hepatitis virus carrier, hepatic cirrhosis, hepatic steatosis, others (These should be tabulated by using categories of “without liver disorders,” “with liver disorders,” and “undescribed” in the table that is not requiring tabulation by the above disposition)
Complication: liver disorders (hepatitis)	Hepatitis B, other, undescribed
Complication: liver disorders (hepatitis virus carrier)	Hepatitis B., others, undescribed
Complication: renal disorders	Nephritis, renal failure, nephrotic syndrome, others (These should be tabulated by using categories of “without renal disorders,” “with renal disorders,” and “undescribed” in the table that is not requiring tabulation by the above disposition)
Complication: cardiovascular disorders	Cardiac failure, angina pectoris, arrhythmia, hypertension, others (without cardiovascular disorders, with cardiovascular disorders, undescribed)
Complication: blood disorders	Anaemia, aplastic anaemia, pancytopenia, others

Data	Layer separation
	(These should be tabulated by using categories of “without blood disorders,” “with blood disorders,” and “undescribed” in the table that is not requiring tabulation by the above disposition)
Complication: respiratory disorders	Interstitial pneumonia, asthma, obstructive pulmonary disease, bronchitis bacterial, nontuberculous mycobacteriosis (including colonization), others (These should be tabulated by using categories of “without respiratory disorder,” “with respiratory disorder,” and “undescribed” in the table that is not requiring tabulation by the above disposition)
Complication: others	Diabetes mellitus, gastrointestinal disorder, osteoporosis, malignant tumour, demyelinating disorders, collagen disorders (other than rheumatoid arthritis), others (These should be tabulated by using categories of “without others,” “with others,” and “undescribed” in the table that is not requiring tabulation by the above disposition)
Past history	Present, absent, unknown, undescribed
Past history: details	Tuberculosis, nontuberculous mycobacteriosis, interstitial pneumonia, bronchitis bacterial, obstructive pulmonary disease, aplastic anaemia, pancytopenia, malignant tumour, demyelinating disorders, surgery for RA, others
History of allergy	Present, absent, unknown, undescribed
History of allergy: details	Drug, food, both, others
Smoking history	Present, absent, unknown, undescribed
Smoking history: details	Previously, currently, unknown, undescribed
RA stage/progression	Stage I, Stage II, Stage III, Stage IV, undescribed (It also should be tabulated by means of categories of “Stage I + II,” “Stage III + IV” and “undescribed” other than the above categories)
Disability level of RA	Class I, Class II, Class III, Class IV, undescribed (It also should be tabulated by means of categories of “Class I + II,” “Class III + IV” and “undescribed” other than the above categories)
Previous medication: DMARDs	Methotrexate (MTX), salazosulfapyridine, tacrolimus hydrate, bucillamine, others
Dose of concomitant MTX (mg/week) *1	$\geq 12.0\text{mg/week}$ and $< 14.0\text{mg/week}$, $\geq 14.0\text{mg/week}$ and $< 16.0\text{mg/week}$, $\geq 16.0\text{mg/week}$
Concomitant drug: DMARDs (other than MTX) *1	Present, absent
Concomitant drug: adrenocortical hormone *1	Present, absent

Data	Layer separation
Concomitant drug: DMARDs (other than MTX) *2	Present, absent
Concomitant drug: adrenocortical hormone *2	Present, absent
Concomitant drug: other concomitant drugs *2	Present, absent
DAS28-4CRP at Baseline by Category *3	<2.6, 2.6<=

*1 The concomitant drugs used at the start of Humira treatment should be included.

*2 The concomitant drugs used during the treatment with Humira should be included.

*3 The layer separation at the time of logistic regression analysis in the literature analysis should be applied.

<Treatment status>

Data	Layer separation
Mode of administration	Administration by a physician only, self-administration only, administration by a physician and self-administration
Period to treatment completion (day)*	≤ 168, ≥ 169 and ≤ 364, ≥ 365 and ≤ 728, continuing treatment *Continuing treatment should be ≥ 729 or the continued patients in the third CRF.
Dosage and administration	40 mg/biweekly, 80 mg/2 biweekly, 40 mg/biweekly or 80 mg/biweekly, other

* Patients confirmed to have longer treatment duration than 728 days and with “continuing” in the final record in the “treatment status” in the third CRF should be specified as the category of “continuing treatment.”

<Reason for discontinuation>

Data	Layer separation
Reason for discontinuation (first and second CRFs)	Occurrence of AEs, inadequate response, patient refused treatment with Humira, failed to visit hospital, others [symptoms improved (including complete remission), pregnancy/desire for pregnancy, others], undescribed
Reason for discontinuation (third CRF)	Occurrence of AEs, symptom improved, inadequate response, patient refused treatment with Humira, others (pregnancy/desire for pregnancy, others), undescribed
Reason for survey discontinuation	Administration of biological products other than Humira, failed to visit hospital, others, undescribed

<Efficacy endpoints>

Data	Layer separation	
DAS28-4ESR	High Moderate Low Remission	> 5.1 > 3.2 and ≤ 5.1 ≥ 2.6 and ≤ 3.2 < 2.6
DAS28-4CRP	High Moderate Low Remission	> 5.1 > 3.2 and ≤ 5.1 ≥ 2.6 and ≤ 3.2 < 2.6
CDAI	High Moderate Low Remission	> 22.0 > 10.0 and ≤ 22.0 > 2.8 and ≤ 10.0 ≤ 2.8
SDAI	High Moderate Low Remission	> 26.0 > 11.0 and ≤ 26.0 > 3.3 and ≤ 11.0 ≤ 3.3
HAQ-DI	High Moderate Low Remission	> 1.5 > 1.0 and ≤ 1.5 > 0.5 and ≤ 1.0 ≥ 0 and ≤ 0.5
mTSS	Change (≤ 0) Change (≤ 0.5) Change (≤ 1.0)	Change ≤ 0 Change ≤ 0.5 Change ≤ 1.0
Bone erosion score	Change (≤ 0) Change (≤ 0.5) Change (≤ 1.0)	Change ≤ 0 Change ≤ 0.5 Change ≤ 1.0
Joint space narrowing score	Change (≤ 0) Change (≤ 0.5) Change (≤ 1.0)	Change ≤ 0 Change ≤ 0.5 Change ≤ 1.0

*Hereafter, “complete remission” refers to “Remission” in the above table.

12. Handling of data on test/evaluation time

For data entered at each timing of efficacy evaluation excluding mTSS, bone erosion score and joint space narrowing score, the acceptability of data by timing should be judged based on the acceptable range of the timing. The acceptable range of the timing is shown in the table below.

If there is more than one data within the acceptable range of the timing, the data on the closest date to the reference date should be adopted. If there is more than one data within the acceptable range of the timing with the equal number of days from the reference before and after the reference date respectively, the data before the reference date should be adopted.

When evaluating efficacy regarding administration of Humira, it should follow the following provision for the data included in the following acceptable range.

- The data up to the date of final Humira treatment + 28 days should be tabulated.

However, the date of final Humira treatment +28 days is later than the date of survey discontinuation, the data up to the date of survey discontinuation should be tabulated.

This date is called [final evaluation date] in the following.

Timing and period category	Handling of data
Prior to treatment start	Data included in the period between the date of initial Humira treatment -28 days and the date of initial Humira treatment and the closest data to the date of initial Humira treatment should be adopted.
At week 12	Data included in the period between the date of initial Humira treatment +56 days and the date of initial Humira treatment +112 days and the closest data to the date of initial Humira treatment +84 days should be adopted.
At week 24	Data included in the period between the date of initial Humira treatment +140 days and the date of initial Humira treatment +196 days and the closest data to the date of initial Humira treatment +168 days should be adopted.
At week 52	Data included in the period between the date of initial Humira treatment +336 days and the date of initial Humira treatment +392 days and the closest data to the date of initial Humira treatment +364 days should be adopted.
At week 76	Data included in the period between the date of initial Humira treatment +504 days and the date of initial Humira treatment +560 days and the closest data to the date of initial Humira treatment +532 days should be adopted.
At week 104	Data included in the period between the date of initial Humira treatment +700 days and the date of initial Humira treatment +756 days and the closest data to the date of initial Humira treatment +728 days should be adopted.
At final evaluation	The final data of the patient among the data included in the period between the date of initial Humira treatment +1 day and the final evaluation date should be adopted.

For data entered at each evaluation timing of mTSS, bone erosion score and joint space narrowing score when evaluating efficacy regarding administration of Humira, the acceptability of data by timing should be judged based on the acceptable range of the timing. The acceptable range of the timing is shown in the table below.

If there is more than one data within the acceptable range of the timing, the data on the closest date to the reference date should be adopted. If there is more than one data within the acceptable range of the timing with the equal number of days from the reference before and after the reference date respectively, the data before the reference date should be adopted.

Additionally, it should follow the following provision for the data included in the following acceptable range.

- If the date up to the date of final Humira treatment +56 days, and the date of survey discontinuation is later than the date of survey discontinuation +56 days, the data up to the date of survey discontinuation should be tabulated.

Timing and period category	Handling of data
Prior to treatment start	Data included in the period between the date of initial Humira treatment -56 days and the date of initial Humira treatment +56 days and the closest data to the date of initial Humira treatment should be adopted.
At week 52	Data included in the period between the date of initial Humira treatment +308 days and the date of initial Humira treatment +420 days and the closest data to the date of initial Humira treatment +364 days should be adopted.
At week 104	Data included in the period between the date of initial Humira treatment +672 days and the date of initial Humira treatment +784 days and the closest data to the date of initial Humira treatment +728 days should be adopted.

The time for evaluation of treatment continuing group and treatment discontinued group in the third CRF should also be allocated separately. For patients whom the final Humira treatment is later than week 52 +4 weeks, the data on the latest date in the third CRF should be used as the data on the final evaluation date. However, if there is the date of survey discontinuation, the data up to the date should be used.

This date is called [final evaluation date] in the following.

At final evaluation (third CRF)	
When the date of survey discontinuation is not entered: The last data of the patient among the data included in the period between the date of initial Humira treatment +504 days and the final evaluation date should be adopted.
 
When the date of survey discontinuation is entered: The last data of the patient among the data included in the period between the date of initial Humira treatment +504 days and the final evaluation date should be adopted.

---------------------------------	---

	In the treatment discontinued group, the data of which the date of treatment discontinuation and the final evaluation date are ≥ 24 weeks apart should be adopted.
--	---

